For safety evaluations, the last available assessment, including unscheduled assessments before the date of start of study treatment is taken as “baseline” assessment.

For pre-dose electrocardiogram (ECG), the last available assessment before the treatment start date/time is used for baseline.

For ECGs, where study requires multiple replicates per time point, the average of these measurements would be calculated for baseline (if not already available in the database).

For mutations, the Week 1 Day 1 assessment is taken as “baseline” assessment.

In rare cases where multiple laboratory measurements meet the baseline definition, with no further flag or label that can identify the chronological order, then the following rule should be applied: If values are from central and local laboratories, the value from central assessment should be considered as baseline.

If patients have no value as defined above, the baseline result will be missing.

Baseline for the treatment switch period

For subjects switching from bosutinib to asciminib, the last non-missing assessment, including unscheduled assessments before the date of first administration of asciminib is taken as “baseline” assessment for the switched treatment period, and denoted as baseline_switch for short.

On-treatment assessment/event and observation periods

For adverse event reporting the overall observation period will be divided into three mutually exclusive segments for subjects without treatment switching and into up to five mutually exclusive segments for subjects switching treatment:

For subjects without treatment switching:

1. **pre-treatment period:** from day of patient’s informed consent to the day before first administration of study treatment (FD)

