2. **on-treatment period:** from date of first administration of study treatment to 30 days after date of last actual administration of study treatment (including start and stop date) (LD). Note: Patients will be treated up to the end of study treatment period (EOsT). This will be the last actual administration of study treatment for each patient if the patient has not discontinued study treatment earlier. On this date, all patients without treatment switching will have been treated for at least 96 weeks unless patients have discontinued study treatment earlier. After this period, the assigned study treatment will be made available, may be outside of this study, to patients who in the opinion of the investigators are still deriving clinical benefit.
3. **post-treatment period:** starting at day 31 after last administration of study treatment.

For subjects with treatment switching from bosutinib to asciminib:

- **pre-treatment period:** from day of patient's informed consent to the day before first administration of study treatment (FD)
- **on-treatment period:** from date of first administration of study treatment to either the day before the first administration of asciminib (FD_{switch}) or 30 days after the date of last actual administration of bosutinib (LD), whichever comes first.
- **post-treatment period:** from day 31 after last administration of bosutinib to the day before the first administration of asciminib (FD_{switch}). If the end date is before the start date, this period is not applicable.
- **on-switched treatment period:** from date of first administration of asciminib (FD_{switch}) to 30 days after date of last actual administration of asciminib (LD_{switch}).
NOTE: Subjects are treated in the study up to end of study treatment period (EOsT). On this date, all subjects with treatment switching will have been treated for at least 48 weeks after switching unless they have discontinued the switched treatment earlier.
- **Post-switched treatment period:** from day 31 after last actual administration of asciminib (LD_{switch}).

If dates are incomplete in a way that clear assignment to pre-, on-, post-, on-switched-, post-switched-treatment period cannot be made, then the respective data will be assigned to the on-treatment period.

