Safety summaries (tables, figures) on the Safety set (respectively on the Switch Analysis Set) include only data from the on-treatment (resp. on-switched treatment) period with the exception of baseline data which will also be summarized where appropriate (e.g. change from baseline summaries). In particular, summary tables for adverse events (AEs) will summarize only on-treatment (resp. on-switched treatment) events, with a start date during the on-treatment (resp. on-switched treatment) period (**treatment-emergent** AEs) (resp. switched-treatment-emergent AEs). In addition, a separate summary for death including on-treatment and post-treatment deaths will be provided.

However, all safety data (including those from the pre-treatment, post-treatment and post-switched treatment period) will be listed and flagged as appropriate.

Efficacy summaries on the FAS (apart from OS and PFS) include data from baseline up to either the last assessment on or before the EoT visit or before or on treatment failure, whichever is the earliest.

Efficacy summaries on the Switch Analysis Set include data from baseline_switch up to the last assessment on or before the S-EoT visit or before or on treatment failure during the switched treatment period, whichever is the earliest.

The efficacy assessments collected post-treatment failure, post-EoT or post S-EoT visit are not included in any efficacy analyses (except for OS and PFS analyses). However, they will be listed and flagged as appropriate.

Windows for multiple assessments

Data such as molecular response, cytogenetic response collected over time (including unscheduled visits) will be summarized by scheduled time point. As patients do not always adhere to the visit schedule, visits will be remapped according to visit windows defined in Tables 2-1 to Table 2-4 of this document to enable by-visit analysis. Only those protocol-defined visits will have the visit window defined. Each assessment (including the end of treatment assessment), either scheduled or unscheduled, will have a mapped visit assigned, as long as study day is available, according to the defined visit window up to the date with data included.

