2.8.3 Laboratory data

Grading of laboratory values will be assigned programmatically as per National Cancer Institute (NCI) Common Terminology Criteria for Adverse Events (CTCAE) version 4.03. The calculation of CTCAE grades will be based on the observed laboratory values only, clinical assessments will not be taken into account. CTCAE Grade 0 will be assigned for all non-missing values not graded as 1 or higher. Grade 5 will not be used. Details of CTCAE grading and imputation rules are presented in [Appendix 5.3](#).

For laboratory tests where grades are not defined by CTCAE v4.03, results will be categorized as low/normal/high based on laboratory normal ranges.

On analyzing laboratory data, all sources (central and local laboratories) will be combined. The summaries will include all assessments available for the lab parameter collected no later than 30 days after the last study treatment administration date.

The following summaries will be produced on the Safety set separately for hematology and biochemistry laboratory data (by laboratory parameter and treatment):

- Worst post-baseline CTCAE grade (regardless of the baseline status). Each subject will be counted only for the worst grade observed post-baseline in the on-treatment period.
- Shift tables using CTCAE grades to compare baseline to the worst on-treatment value.
- For laboratory tests where CTCAE grades are not defined, shift tables using the low/normal/high/(low and high) classification to compare baseline to the worst on-treatment value.

The same summaries will be produced on the Switch Analysis Set for the on-switched treatment period.

The following listings will be produced separately for hematology and biochemistry for the laboratory data:

- Listings of all laboratory data, with CTCAE grades and classification relative to the laboratory normal range. Lab data collected during the post-treatment period will be flagged.
- Listing of all CTCAE grade 3 or 4 laboratory toxicities

Liver function parameters

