2.8.4.3 Vital signs

Vital sign assessments are performed in order to characterize basic body function. The following parameters were collected: height (cm), weight (kg), body temperature ($^{\circ}\text{C}$), heart rate (beats per minute), systolic and diastolic blood pressure (mmHg).

Data handling

Vital signs collected on treatment will be summarized. Values measured outside of on treatment period will be flagged in the listings.

Data analysis

The number and percentage of subjects with notable vital sign values (high/low) in systolic blood pressure, diastolic blood pressure, pulse rate, weight and temperature will be presented by treatment arm.

A listing of all vital sign assessments will be produced by treatment arm and notable values will be flagged. In the listing, the assessments collected outside of on-treatment period will be flagged.

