BCR-ABL1 gene mutation	W1D1 pre-dose and end of treatment. If mutation is present at baseline, then also every 12 weeks after baseline	Peripheral blood	Sanger Sequencing
Low level mutations in BCR-ABL1 gene	W1D1 pre-dose and end of treatment	Peripheral blood	Mass spectrometry and NGS
Circulating cytokines in plasma	W1D1 pre-dose, Week 48 and end of treatment	Peripheral blood	MSD and ELISA
Genetic variant analysis of the UGT2B7 and UGT2B17 gene	W1D1	Peripheral blood	Genechip

General data handling and preprocessing

For bone marrow samples the latest assessment during screening period will be used as the baseline value, while for blood samples the week 1 day 1 (W1D1) pre-dose assessment will be used as the baseline value.

When more than one biomarker data value are available for a subject at any time point, the mean of the replicate values will be used for all statistical analyses.

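### Laboratory and vital-sign values taken pre-dose on the first-dose date cannot be safety baseline and are counted as on-treatment findings

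*Combined protocol and SAP*

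**What the plan says.** All references are to the SAP addendum 1.0 (14-Oct-2020). The same baseline and period rules stand in the pre-lock SAP amendment 3.0.

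- **General safety baseline** (Section 2.1.1, Baseline for the treatment period): "the last available assessment, including unscheduled assessments before the date of start of study treatment is taken as" baseline. The cut is by date and is strict. A patient with no qualifying value has a missing baseline.
- **Pre-treatment period** (Section 2.1.1): runs from consent "to the day before first administration of study treatment (FD").
- **On-treatment period** (Section 2.1.1): "from date of first administration of study treatment to 30 days after date of last actual administration of study treatment (including start and stop date"). This is also set by date, with no clock time.
- **Data used**: safety summaries "include only data from the on-treatment (resp. on-switched treatment) period with the exception of baseline data".
- **Laboratory tables** (Section 2.8.3): "Each subject will be counted only for the worst grade observed post-baseline in the on-treatment period". The shift tables compare baseline with the worst on-treatment value, and the liver criteria use worst post-baseline values.
- **Vital signs** (Section 2.8.4.3): "Vital signs collected on treatment will be summarized", as counts of notable high or low values that include weight.
- **Exceptions**: ECG baseline is cut by treatment start date and time. Mutation baseline is the Week 1 Day 1 assessment. In Section 2.13, "for blood samples the week 1 day 1 (W1D1) pre-dose assessment will be used as the baseline value".
- **Switch phase** (Section 2.1.1): baseline_switch takes only assessments dated before the first asciminib date, and the on-switched period begins on that date. The ECG date/time sentence sits under the treatment-period heading and is not repeated for the switch.

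**The concern.** A sample drawn before the first dose cannot show an effect of that dose. Under these rules such a sample, if taken on the dosing day, falls outside baseline and inside the on-treatment period. Two things then go wrong. The value becomes eligible to be the patient's worst on-treatment result. And the baseline used in its place is an older one, or missing if none exists.

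The plan deals with exactly this case for ECG, mutations and blood biomarkers. Laboratory data and vital signs have no such provision.

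The switch phase deserves particular attention. Safety of asciminib after bosutinib failure is a secondary objective (Table 1-1), and the Switch Analysis Set has no comparator. Section 2.1.1 allows for bosutinib as bridging therapy between treatment failure and the first asciminib dose. A pre-dose abnormality on the first asciminib date may therefore reflect bosutinib, yet it would be tabulated as an on-switched asciminib finding.

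**Working it through.** The plan gives no figure to reproduce here. The check is on date logic.

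**Inputs.** Let d = assessment date minus date of first dose (FD), and let LD be the number of days from FD to last dose. From Section 2.1.1:

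- General safety baseline: d < 0.
- ECG-type baseline: d < 0, or d = 0 and before the dose.
- On-treatment: 0 ≤ d ≤ LD + 30.
- Study day: d + 1 if d ≥ 0, otherwise d.

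**Classification.**

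| Assessment | Study day | Baseline under the general rule | On-treatment by date | Baseline under an ECG-type rule |
|---|---|---|---|---|
| d = −7 | −7 | eligible | no | eligible |
| d = −1 | −1 | eligible | no | eligible |
| d = 0, pre-dose | 1 | **not eligible** | **yes** | eligible |
| d = 0, post-dose | 1 | not eligible | yes | not eligible |
| d = +1 | 2 | not eligible | yes | not eligible |

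The only misclassified row is the pre-dose value on the first-dose date. The ECG-type rule classifies all five rows correctly. A plain cut at d ≤ 0 would recover that row but would also make the d = 0 post-dose value eligible as baseline.

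**Which tables.** The affected outputs are those that take a worst or notable value from the on-treatment period under the general rule: laboratory worst grade, laboratory shifts, liver thresholds (Section 2.8.3) and notable vital signs including weight (Section 2.8.4.3).

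**Bound on size.** For a given threshold, let A be the proportion of patients whose worst value crosses it when the pre-dose sample is counted, and B the proportion when it is not. A − B is the proportion whose pre-dose sample crosses the threshold while no later on-treatment value does. That cannot exceed the share of patients whose worst value is that sample. It is zero for any parameter not measured pre-dose on that date. In a shift table the baseline category can also change, wherever the grade on the first-dose date differs from the earlier grade.

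**Switch phase.** Replace FD with the first asciminib date. baseline_switch is d < 0 and the on-switched period starts at d = 0, so the same row is misclassified. With no date/time rule stated there, it also applies to ECG, and Section 2.8.4.1 tabulates notable ECG values for the switch set.

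**The case against.** The strongest reply is that the premise may rarely be met. The visit schedule is not in the part of the document available. The only safety measurement that this part places on Week 1 Day 1 is weight, in the summary of changes for protocol amendment 2. That limit stands: the defect in the rule is certain, but its reach is not known.

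A second reply is that the rule is the same in both arms, the tables are descriptive, and the primary and key secondary endpoints are untouched. This is also true and keeps the point modest. It does not answer the switch phase, which has no second arm.

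A third is that the strict cut has a purpose, since it keeps same-day post-dose values out of baseline. That is a fair argument against a plain on-or-before rule, and none against the date/time rule already used for ECG.

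Four stronger readings are tempting, and the documents do not support them.

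- **Vital-sign shifts.** A reader might infer that vital signs and weight enter worst-grade or shift tables. Section 2.8.4.3 plans only notable-value counts and a listing.
- **Change from baseline.** A reader might infer distorted laboratory change-from-baseline summaries. None is listed. Those specified are for ECG, which has its own rule in the randomized phase, and for LVEF, summarised at baseline and Week 20.
- **A numerical inflation.** A reader might suppose that 3 to 10% of patients have their worst grade on that sample and read this as a rise of 3 to 10 points in toxicity rates. The documents give no such share. Even if it were granted, it would be a ceiling on a worst-grade or threshold count.
- **Untreated values at the switch.** A reader might call the switch-date value drug-free. With bosutinib bridging it may not be, and the issue is then attribution between two drugs.

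**Conclusion.** The point holds as a gap between two date rules. The general safety baseline stops the day before first dose, the on-treatment period starts on the day of first dose, and nothing in the text available returns a pre-dose value from that day to baseline. The same gap exists at the first asciminib date, where ECG is not protected either.

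Its size cannot be stated. It depends on which parameters are measured pre-dose on those dates and on how often that value is a patient's worst, and neither is in the documents shown. A claim that toxicity rates are overstated in both arms must stay conditional on such sampling. Onset of adverse events on the first-dose date is a separate date convention and is not challenged.

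One further limit applies. The document ends with a change log that is followed by no SAP text, so any later rule could not be checked. A correction is worthwhile, because it is cheap and the 96-week and end-of-study-treatment analyses come after this addendum.

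**What to change.** 1. Extend the ECG date/time rule to all safety baselines, so that baseline is the last assessment before the recorded date and time of first dose.
2. Where no time is recorded, treat an assessment scheduled as pre-dose on the first-dose date as baseline, and treat any other untimed value from that date as on-treatment. This avoids admitting untimed post-dose values to baseline.
3. Exclude the values identified as pre-dose from the on-treatment and on-switched summaries.
4. Apply the same three rules to baseline_switch at the first asciminib dose, and name ECG explicitly there.

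The cost is a short SAP amendment, re-derivation of the baseline flag, and a rerun of the affected safety tables for the 96-week and end-of-study-treatment analyses. No new data are needed. The primary database is already locked, so the primary-analysis tables could be re-derived as a check and any differences reported.

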For efficacy evaluations, the last non-missing assessment, including unscheduled assessments on or before the date of randomization is taken as “baseline” value or “baseline” assessment. In the context of baseline definition, the efficacy evaluations also include PRO and performance status.

For safety evaluations, the last available assessment on or before the date of start of study treatment is taken as “baseline” assessment.

For pre-dose electrocardiogram (ECG), the last available assessment before the treatment start date/time is used for baseline.

For ECGs, where study requires multiple replicates per time point, the average of these measurements would be calculated for baseline (if not already available in the database).

In rare cases where multiple laboratory measurements meet the baseline definition, with no further flag or label that can identify the chronological order, then the following rule should be applied: If values are from central and local laboratories, the value from central assessment should be considered as baseline.

If patients have no value as defined above, the baseline result will be missing.

On-treatment assessment/event and observation periods

For adverse event reporting the overall observation period will be divided into three mutually exclusive segments:

1. ***pre-treatment period***: from day of patient’s informed consent to the day before first administration of study treatment
2. ***on-treatment period***: from date of first administration of study treatment to 30 days after date of last actual administration of any study treatment (including start and stop date). Note: Patients will be treated for up to LPFT + 96 weeks. This will be the last actual administration of study treatment for each patient if the patient has not discontinued study treatment earlier. After this period, the assigned study treatment will be made available, may be outside of this study, to patients who in the opinion of the investigators are still deriving clinical benefit.
3. ***post-treatment period***: starting at day 31 after last administration of study treatment.

If dates are incomplete in a way that clear assignment to pre-, on-, or post-treatment period cannot be made, then the respective data will be assigned to the on-treatment period.

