5.1.2 AE, ConMeds and safety assessment date imputation

The imputations specified in this section are only used for analyses of time to and duration of AEs and concomitant medications.

Table 5-1 Imputation of start dates (AE, CM) and assessments (LB, EG, VS)

Missing Element	Rule
day, month, and year	
 No imputation will be done for completely missing dates
day, month	
 If available year = year of study treatment start date then 
 If stop date contains a full date and stop date is earlier than study treatment start date then set start date = 01JanYYYY Else set start date = study treatment start date. If available year > year of study treatment start date then 01JanYYYY If available year < year of study treatment start date then 01JulYYYY
day	
 If available month and year = month and year of study treatment start date then 
 If stop date contains a full date and stop date is earlier than study treatment start date then set start date= 01MONYYYYY. Else set start date = study treatment start date. If available month and year > month and year of study treatment start date then 01MONYYYYY If available month and year < month year of study treatment start date then 15MONYYYYY

Table 5-2 Imputation of end dates (AE, CM)

Missing Element	Rule (* = last treatment date plus 30 days not > (death date, cut-off date, withdrawal of consent date))
day, month, and year	
 Completely missing end dates (incl. ongoing events) will be imputed by the end date of the on-treatment period*
day, month	
 If partial end date contains year only, set end date = earliest of 31DecYYYY or end date of the on-treatment period *
day	
 If partial end date contains month and year, set end date = earliest of last day of the month or end date of the on-treatment period*

Any AEs and ConMeds with partial/missing dates will be displayed as such in the data listings.

Any AEs and ConMeds which are continuing as per data cut-off will be shown as 'ongoing' rather than the end date provided.

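### For patients who switch to asciminib, safety records with ambiguous partial dates default to the bosutinib period, even when onset can only have followed the switch

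*Combined protocol and SAP*

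**What the plan says.** The sentence is in section 2.1.1 of the latest full SAP text shown (addendum 1.0, October 2020) and, unchanged, in amendment 3.0. It opens with a condition, that the date is too incomplete for a clear assignment, and ends with a single destination for all patients: where assignment to a pre-, on-, post-, "on-switched-, post-switched-treatment period cannot be made, then the respective data will be assigned to the on-treatment period".

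For switchers, the same section defines on-treatment as running "from date of first administration of study treatment to either the day before the first administration of asciminib" "or 30 days after the date of last actual administration of bosutinib (LD), whichever comes first". It is therefore a bosutinib period. The on-switched period is separate, "from date of first administration of asciminib (FD_{switch}) to 30 days after date of last actual administration of asciminib".

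The period decides the table. Adverse event summaries on the Safety Set, and on the Switch Analysis Set respectively, "will summarize only on-treatment (resp. on-switched treatment) events". Section 2.8 confirms that safety in the switched period is summarised on the Switch Analysis Set.

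The date imputation in section 5.1.2 is limited to time-to and duration analyses. Table 5-1 is anchored on the start of study treatment and never mentions the first asciminib dose after the switch. Table 5-2 says: "Completely missing end dates (incl. ongoing events) will be imputed by the end date of the on-treatment period". An asterisk on that entry defines the end as the last treatment date plus 30 days, capped by death, cut-off or withdrawal of consent.

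**The concern.** The August 2017 SAP had three periods and no switch phase, so sending a doubtful date to on-treatment was cautious: the event counted against the drug that the patient was taking. When the switch phase was added, the list of periods in the sentence grew from three to five but the destination stayed the same. For a switcher, the rule now charges a doubtful event to the drug that was stopped and takes it away from the drug that was started.

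Two outputs are touched. One is the safety of asciminib after bosutinib failure, which Table 1-1 lists as a secondary objective. The other is the bosutinib column of the main safety comparison.

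**Working it through.** The plan states no figure on this point, so the check applies the definitions to example dates.

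**Step 1: periods for one hypothetical switcher (assumed dates).** Bosutinib from 1 March 2019 to 10 March 2020; asciminib from 16 March 2020 to 15 June 2021.
- On-treatment ends at the earlier of the day before first asciminib (15 March 2020) and last bosutinib + 30 days (9 April 2020), so on 15 March 2020.
- On-switched runs from 16 March 2020 to 15 June 2021 + 30 days = 15 July 2021.
- Post-switched starts on 16 July 2021.

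**Step 2: apply the rule to partial onset dates.**

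| Onset recorded as | Periods possible | Assigned to | Comment |
|---|---|---|---|
| October 2019 | on-treatment | on-treatment | correct |
| March 2020 | on-treatment, on-switched | on-treatment by default | may have begun on either drug |
| 2020 only | on-treatment, on-switched | on-treatment by default | may have begun on either drug |
| September 2020 | on-switched | on-switched | correct |
| July 2021 | on-switched, post-switched | on-treatment by default | impossible |
| 2021 only | on-switched, post-switched | on-treatment by default | impossible |
| 2022 only | post-switched | post-switched | correct |

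The default is reached only where a partial date crosses a period boundary. In the two rows marked impossible, the assigned period ended more than nine months before the earliest possible onset.

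**Step 3: compare with Table 5-1.** Take last asciminib on 10 February 2021, so that on-switched ends on 10 February + 30 days = 12 March 2021, and an onset recorded as March 2021. Table 5-1 imputes 1 March 2021, which lies inside the on-switched period. Section 2.1.1 files the same event under bosutinib. Table 5-1 does not override this, because it serves only time-to and duration analyses.

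**Step 4: scale.** SAP section 3.1 plans 74 bosutinib patients. That figure reproduces: the two-proportion formula without continuity correction, at 15% versus 35%, two-sided 5% alpha, 90% power and 2:1 allocation, gives 74 + 148 = 222. Section 2.8.1 counts a patient once per adverse event category. So, per misassigned patient:
- Bosutinib column: +1/74 = 1.35 percentage points, if the patient has no other event of that category in the on-treatment period.
- Switch Analysis Set: −1/n_switch, if the patient has no other event of that category in the on-switched period. The documents do not give n_switch. Assuming 15 to 30 switchers, this is 1/15 = 6.7 to 1/30 = 3.3 points.

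The number of ambiguous dates is not given either, so no total can be computed.

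**The case against.** The strongest reply is that this is a narrow drafting gap. Much of that reply stands, and it rules out four stronger readings that a reader might infer.

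- *All incompletely dated safety data of switchers go to bosutinib.* They do not. The condition in the sentence limits it to dates that cannot be placed, and a month lying wholly on asciminib is assigned to asciminib.
- *The error always favours asciminib.* This is not shown. An onset that straddles the switch may truly have begun on bosutinib, in which case the default is right. For patients randomized to asciminib, the same default pulls doubtful pre- or post-treatment events into asciminib's own column. Only dates ambiguous between on-switched and post-switched are certain to be misplaced.
- *Every event of that kind shifts the rates.* The shifts in step 4 need the patient to have no other event of the category in the table concerned.
- *Table 5-2 gives switch-phase events an end date before their onset.* The asterisk uses the last treatment date plus 30 days and does not say whether, for switchers, that means last bosutinib or last switched asciminib. With the latter, no negative duration arises. Section 2.1 also says that end dates of ongoing events are not imputed, and sections 2.8.1 and 2.8.1.1 describe no analysis of adverse event duration. This is an undefined term, not a demonstrated error.

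It is also fair that these are descriptive safety summaries, that all safety data are listed and flagged, and that partial dates are displayed as recorded. The protocol body and the adverse event form are not in the part shown, so a phase indicator that would settle many cases cannot be excluded.

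None of this repairs the sentence itself. It has one destination for all patients, and for some switcher records that destination is a period in which the event cannot have occurred.

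**Conclusion.** Wrong as written, for switchers only. The default sends partial onset dates that straddle the switch to bosutinib and drops them from the Switch Analysis Set. It also sends to bosutinib dates ambiguous only between on-switched and post-switched, which is an impossible assignment. Other partial dates and non-switchers are handled acceptably.

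The likely total effect is small and cannot be quantified from the documents. The per-patient figures rest on the planned 74 bosutinib patients, an assumed 15 to 30 switchers, and no other event of the same category. The correction is worth making because the switch-period summary answers a stated secondary objective in what may be a small set, where one patient can move a rate by several points.

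**What to change.** Add a default for switchers to section 2.1.1:

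1. If the partial date cannot precede the first asciminib dose (FD_switch) and is compatible with the on-switched period, assign the record to the on-switched period.
2. If the partial date straddles FD_switch, assign it to one stated period and run a sensitivity summary with the other assignment. On-switched is the cautious choice for the investigational drug.
3. Otherwise, keep the present default.

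Each record stays in one period per summary, which preserves the mutually exclusive segments of section 2.1.1; counting a record in both would not.

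In Tables 5-1 and 5-2, state that FD_switch and LD_switch + 30 days are the anchors for records starting on or after FD_switch. This clarifies an undefined term.

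The cost is a few lines of SAP text, minor programming and one extra summary, best settled before the 96-week and end-of-study-treatment analyses. The downside is that a few events that began on bosutinib may be counted under switched asciminib; the sensitivity summary shows how much that matters.
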